7.4 Procedures for AE and SAE Collection and Reporting

7.4.1 Reporting of Adverse Events

The investigator is responsible for ensuring that all adverse events observed by the investigator or reported by the subject that occur from enrollment (ie, radiation therapy consultation) through 3 months after RT are monitored and reported. After 3 months, targeted adverse events including (eg, neurological, hematological, infections, autoimmune disorders, and secondary malignancies) will be monitored and reported for 6 months after treatment with axicel or tisacel or until disease progression, whichever occurs first.

The investigator must address the below for adverse events:

- Adverse event diagnosis or syndrome (if not known, signs or symptoms)
- Dates of onset and resolution
- Severity
- Assessment of relatedness to investigational product, lymphodepleting chemotherapy or study procedures
- Action taken

In reviewing adverse events, investigators must assess whether the adverse event is possibly related to 1) CAR T cell therapy product 2) RT, or 3) any protocol-required study procedure. The relationship is indicated by a yes or no response and entered into the CRF. A yes response should indicate that there is evidence to suggest a causal relationship between the study treatment or procedure and the adverse event. Additional relevant data with respect to describing the adverse event will be collected in the CRFs.

The investigator is responsible for reviewing laboratory test results and determining whether an abnormal value in an individual study subject represents a clinically significant change from the subject's baseline values. In general, abnormal laboratory findings without clinical significance (based on the Investigator's judgment) are not to be recorded as adverse events. However, abnormal laboratory findings that result in new or worsening clinical sequelae, require therapy or adjustment in current therapy are considered adverse events. Where applicable, clinical sequelae (not the laboratory abnormality) are to be recorded as the adverse event.

The investigator is expected to follow reported adverse events until stabilization or resolution. If a subject begins a new anticancer therapy, the adverse event reporting period for non-serious adverse events ends at the time the new treatment is started.

7.4.2 Reporting of Serious Adverse Events and Non-serious CRS events Grade ≥ 3

The investigator is responsible for reporting all serious adverse events observed by the investigator or reported by the subject that occur after signing of the consent through 3 months after the RT. After 3 months, only serious targeted adverse events (e.g., neurological, hematological, infections, autoimmune disorders, and secondary malignancies) observed by the investigator or reported by the subject will be reported for 6 months after RT or until disease progression, whichever occurs first. For subjects who screen fail or are enrolled but do not receive RT, the reporting period for serious adverse events ends 30 days after the last procedure (e.g., biopsy).

Serious events that the investigator assesses as related to RT should be reported regardless of the study period.

All serious adverse events and non-serious CRS events \geq Grade 3 ²² must be submitted within 24 hours following the investigators knowledge of the event **using a SAE Report Form. Refer to the SAE Report Form for instructions on how to submit the SAE report.** Subsequently, all serious adverse events will be reported to the health authorities per local reporting guidelines.

Progression of the malignancy during the study should not be reported as a serious adverse event. Adverse events associated with disease progression may be reported as serious adverse event. If the malignancy has a fatal outcome within 3 months of the last day of the lymphodepleting therapy,

CAR T infusion, or RT, then the event leading to death must be recorded as a serious adverse event with CTCAE Grade 5.

Death must be reported if it occurs during the serious adverse event reporting period, irrespective of any intervening treatment.

Any death occurring after the first dose of chemotherapy, for the purpose of pre-lymphodepletion, and within 3 months of the CAR T infusion or RT, regardless of attribution to treatment, requires expedited reporting within 24 hours. Any death occurring greater than 3 months after the CAR T infusion or RT requires expedited reporting within 24 hours only if it is considered related to treatment.

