Diagnosis and selection criteria: refractory hematologic malignancy following CAR T cell therapy

Inclusion Criteria

1. Patients must be able to undergo biopsy. Biopsy will be obtained for patients to exclude possibility of false negative residual FDG avidity on PET/CT that is not substantially increased relative to pre-CAR-T PET/CT. Exceptions are allowed for patients who have clearly progressive disease for whom delaying radiation therapy to obtain a biopsy may worsen outcome (such as cases of cord compression), and for patients for whom the risks of biopsy are high (such as patients with evidence for CNS involvement).

2. Biopsy-confirmed refractory disease within 30-90 days following any CD19-targeted CAR T cell therapy for a hematologic malignancy (these include relapsed or refractory large B-cell lymphoma after two or more lines of systemic therapy, including diffuse large B-cell lymphoma (DLBCL) not otherwise specified, primary mediastinal large B-cell lymphoma, high grade B-cell lymphoma, DLBCL arising from follicular lymphoma, and mantle cell lymphoma). Of note, 'refractory' refers to patients who had early refractory disease after CAR-T cell therapy and not to patients who have received CAR-T for refractory disease, but had complete response to CAR-T cell therapy.
3. At least 1 measurable lesion according to the Lugano criteria¹. Lesions that have been previously irradiated will be considered measurable only if progression has been documented following completion of radiation therapy
4. The following criteria pertain to pattern of progression:
 - Patients may have one refractory lesion without other residual or progressive disease as per PET/CT
 - Patients may have more than one refractory lesion, but with evidence for at least partial response of at least one other lesion as per PET/CT
 - Patients with more than one site of refractory disease without evidence for at least partial response of at least one other lesion are eligible if they are:
 - A. Symptomatic from a refractory lesion (such as cord compression or focal pain) or
 - B. Have disease that can locally affect the spinal canal or brain if left untreated.

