End of Study (primary completion)	Defined as when the last subject is assessed or received an intervention for the purposes of final collection of data for the primary endpoint at Month 6
End of Study (end of trial)	Defined as when the last subject is assessed or received an intervention for evaluation in the study, including survival assessments

Abbreviation or Term	Definition/Explanation
FAS	Full analysis set
FL	Follicular lymphoma
Healthcare Facility	Clinical trial site
HGBCL	High grade B-cell lymphoma
HLH	Hemophagocytic lymphohistiocytosis
IB	Investigator’s Brochure
ICF	Informed consent form
ICU	Intensive care unit
IP	Investigational product
IRB/IEC	Institutional Review Board/Independent Ethics Committee
IRRC	Independent Radiological Review Committee
IWG	International Working Group
KTE-C19/axicabtagene ciloleucel	Autologous T cells transduced with retroviral vector containing anti-CD19 CD28/CD3 zeta chimeric antigen receptor
LTFU	Long-term follow-up
LVEF	Left ventricular ejection fraction
mITT	Modified intent-to-treat
MMSE	Mini-Mental Status Exam
MRI	Magnetic resonance imaging
MSGV1	Murine stem cell virus-based vector
NaCl	Sodium chloride
NCI	National Cancer Institute
NHL	Non-Hodgkin lymphoma
ORR	Objective response rate
OS	Overall survival
PET-CT	Positron emission tomography–computed tomography
PBMC	Peripheral blood mononuclear cell
PMBCL	Primary mediastinal B-cell lymphoma
PD	Progressive disease
PR	Partial response
PRO	Patient Reported Outcome - Common Terminology Criteria for Adverse Events
RCR	Replication-competent retrovirus
SAE	Serious adverse event
scFv	Single chain variable fragment

Abbreviation or Term	Definition/Explanation
SD	Stable disease
SMS	Safety management study
SOA	Schedule of assessment
SUSAR	Suspected unexpected serious adverse reaction
Study Day 0	Defined as the first day that axicabtagene ciloleucel is administered to the subject
TEAEs	Treatment-emergent adverse event
TFL	Transformed follicular lymphoma
ULN	Upper limit of normal
VAS	Visual analogue scale

Study Schema

[figure not shown]

TABLE OF CONTENTS

CLINICAL STUDY PROTOCOL SYNOPSIS	3
Inclusion Criteria	4
Exclusion Criteria	5
1.1 Inclusion of Women and Minorities	6
2. OBJECTIVES	15
2.1 Study Design	15
2.2 Protocol Objectives	16
3. BACKGROUND	16
3.1 Disease Background and Rationale	16
3.2 Radiation Therapy for Refractory Lymphoma/Leukemia Following CAR T Cell Therapy	18
3.3 Correlative Studies Background	19
4. PARTICIPANT SELECTION	20

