12.1 Study Endpoints

Primary Endpoint:

- Rate and severity of RT-related toxicity as per CTCAE v5.0 criteria during RT or within the first 30 days of completing RT.

Secondary Endpoints:

- **Duration of response (DOR):** Among subjects who experience an objective response, DOR is defined as the date of their first objective response (which is subsequently confirmed) to disease progression per Lugano criteria¹ or death regardless of cause. Subjects not meeting the criteria for progression or death by the analysis data cutoff date will be censored at their last evaluable disease assessment date and their response will be noted as ongoing.
- **Objective response rate (ORR) per IRRC:** ORR per IRRC is defined as the incidence of either a complete response or a partial response by Lugano criteria¹ as determined by the IRRC. All subjects that do not meet the criteria for an objective response by the analysis data cutoff date will be considered non-responders.
- **Progression-free Survival (PFS):** PFS is defined as the time from RT completion date to the date of disease progression per Lugano criteria¹ or death from any cause. Subjects not meeting the criteria for progression by the analysis data cutoff date will be censored at their last evaluable disease assessment date.

- **Overall survival (OS):** OS is defined as the time from RT completion to the date of death. Subjects who have not died by the analysis data cutoff date will be censored at their last contact date.

Exploratory Endpoints:

- Levels of anti-CD19 CAR T cells in blood
- Levels of cytokines in serum
- Incidence of anti-axicabtagene ciloleucel antibodies
- Investigation of potential biomarker development based on assessment of blood cells, tumor cells and the proposed actions of the investigational product.

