12.4 Analysis of Primary and Secondary Endpoints

Planned Method of Analysis

The primary analysis of all treated subjects will take place once they have had the opportunity to be followed for 6 months.

Descriptive analyses may occur at any time.

Objective Response Rate

The incidence of objective response and exact 2-sided 95% confidence intervals will be generated.

Duration of Response

The competing-risk analysis method ^{24,25} will be used to estimate the cumulative incidence of relapse. The cumulative incidence of relapse in the presence of non-disease related mortality (the competing risk) will be estimated along with 2-sided 95% confidence intervals at 3-month intervals.

Progression-free Survival

Kaplan-Meier estimates and 2-sided 95% confidence intervals will be generated for progression-free survival time. Estimates of the proportion of subjects alive and progression-free at 3-month intervals will be provided.

Overall Survival

Kaplan-Meier estimates and 2-sided 95% confidence intervals will be generated for OS. Estimates of the proportion of subjects alive at 3-month intervals will be provided.

Safety

Subject incidence rates of adverse events including all, serious, fatal, CTCAE version 5.0 Grade 3 or higher and treatment related AEs reported throughout the conduct of the study will be tabulated by preferred term and system organ class. Changes in laboratory values and vital signs will be summarized with descriptive statistics. The incidence of concomitant medications will be summarized.

Tables and/or narratives of deaths through the long-term follow-up and treatment related SAEs will be provided.

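### The all-cause any, serious and Grade 3+ adverse event rates in 12.4 include events that began before the first RT fraction

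*Combined protocol and SAP*

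**What the plan says.** All references are to the combined protocol and SAP.

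- **Start of collection.** Section 7.4.1 covers adverse events "that occur from enrollment (ie, radiation therapy consultation) through 3 months after RT are monitored and reported". Section 7.4.2 covers serious events "that occur after signing of the consent through 3 months after the RT". Table 2 marks the adverse event row at Screening and again at Enrollment & RT Planning. Section 9.7.2 puts 7 to 14 days of planning before RT begins.
- **Tabulation.** The Safety paragraph of 12.4 gives subject incidence rates for all, serious, fatal, Grade 3 or higher and treatment-related events "reported throughout the conduct of the study will be tabulated by preferred term and system organ class". It sets no condition on onset date.
- **Treatment-emergent rule.** The glossary expands TEAEs as "Treatment-emergent adverse event", but the term is neither defined by date nor used in sections 7 or 12. The Analysis Subsets heading in 12.5 has no text under it.
- **Primary endpoint.** Section 12.1 defines it as "Rate and severity of RT-related toxicity as per CTCAE v5.0 criteria during RT or within the first 30 days of completing RT".
- **Population.** Section 12.4 says: "The primary analysis of all treated subjects will take place once they have had the opportunity to be followed for 6 months".
- **Data on record.** Section 7.4.1 asks for onset and resolution dates, and for a yes/no judgement on relation to the CAR T product, to RT and to study procedures.

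**The concern.** The primary objective is the safety of RT. The all-cause tables are the part of the safety report that does not depend on the investigator's judgement of cause, so a reader will turn to them to check the RT-related figures. If the collection window opens before RT and the tables use the whole window, they mix events that could follow from RT with events that could not.

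Take a subject who has an infection during the planning period and no event afterwards. Under 7.4.1 the infection is collected, and under 12.4 the subject counts as having had an adverse event. If the infection leads to admission, the subject also counts in the serious rate. Adding pre-RT events can only raise these subject incidence rates, never lower them, and with about 20 subjects a few such cases are visible.

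**Working it through.** **1. The plan's own figure.** The documents state no adverse event rate. The only figure that bears on the size of the effect is the number of subjects. Section 12.2 states 19 for a 95% interval of ±10 points in a population of 0.3 × 80 = 24. With n0 = 1.96² × p(1 − p)/0.10² and n = n0/(1 + (n0 − 1)/24):

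- p = 0.5: n0 = 96.04, n = 19.36
- p = 0.3: n0 = 80.67, n = 18.68

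The stated 19 reproduces, and about 20 are to be enrolled. An onset rule does not change this.

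**2. Which outputs can hold a pre-RT event, on the text:**

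| Output | Limit in the text | Pre-RT event can enter? |
|---|---|---|
| Primary endpoint (12.1) | RT-related, and within RT or the 30 days after it | No |
| Stopping rule (12.3) | Attributed to RT | No |
| First pause criterion (7.4.4) | RT-related | No |
| Fatal events (12.4) | None on onset, but a treated subject was alive at the first fraction | No, among treated subjects |
| Any, serious, Grade 3+ events (12.4) | None | Yes |

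**3. Effect of one subject.** 1/20 = 5 percentage points for each subject whose only event in that table precedes RT.

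**4. Effect on event counts.** Inputs: pre-RT time d = 7 to 14 days (9.7.2); follow-up of 3 months after RT, taken as 90 days (7.4.1). Assumptions: RT course L = 1 to 28 days, since the documents leave the course to the treating physician, and a constant event rate. The relative addition is d/(L + 90):

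| | L = 1 | L = 28 |
|---|---|---|
| d = 7 | 7/91 = 7.7% | 7/118 = 5.9% |
| d = 14 | 14/91 = 15.4% | 14/118 = 11.9% |

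The planning period alone therefore adds about 6% to 15%. Targeted events are collected beyond 3 months. For those categories the denominator is longer and the share is smaller.

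**5. Effect on subject incidence.** Let q be the incidence from the first fraction onward and p the chance of a pre-RT event. Both are assumed, as is their independence. The tabulated incidence is 1 − (1 − q)(1 − p). For q = 20% and n = 20:

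| p | Tabulated incidence | Extra subjects of 20 | Chance that at least 1 of 20 has a pre-RT event, 1 − (1 − p)^20 |
|---|---|---|---|
| 5% | 1 − 0.80 × 0.95 = 24% | 0.8 | 64% |
| 10% | 1 − 0.80 × 0.90 = 28% | 1.6 | 88% |
| 20% | 1 − 0.80 × 0.80 = 36% | 3.2 | 99% |

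Over q = 10% to 30% and p = 5% to 20%, the addition runs from 3.5 points (q = 30%, p = 5%) to 18 points (q = 10%, p = 20%). With an onset rule it is zero by construction.

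**The case against.** The strongest reply is that what drives decisions in this trial is already protected. The primary endpoint, the stopping rule and the first pause criterion all need attribution to RT. The 12.4 tables are descriptive, with no test attached, in a single-arm pilot. Onset dates and relatedness are recorded, so the split can be made at reporting. Section 12.5 also refers data handling to a statistical analysis plan and a Trial Integrity Document, which may contain a rule. All of this stands, and it confines the point to the all-cause tables. It does not remove it: 12.4 is the analysis text we have, and read literally it counts pre-RT events.

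A second reply concerns who would have such events. A reader might infer from the eligibility of patients who are "Symptomatic from a refractory lesion (such as cord compression or focal pain) or" (Synopsis, inclusion criterion 4) that many carry a serious event into the tables from the start. The documents do not support that. Section 7.2 excludes a pre-existing condition that has not worsened, and 7.4.2 says progression itself is not a serious event, while events associated with it may be reported as one. Only new or worsening signs and symptoms would count.

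Three further readings are tempting and go too far:

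- **A much larger effect on serious events.** One could add the 28-day screening window and the 14-day planning window in Table 2 to get 42 days before RT. The 28 days is a window for assessments, and 9.7.1 lets standard-of-care procedures precede consent, whereas collection of serious events starts only at consent. The documents give no consent-to-RT interval.
- **Inflation of the fatal rate.** This fails if the tables follow the treated population named in 12.4.
- **A historical comparison biased against RT.** Section 12.5 does compare safety endpoints with patients who had no RT, but it does not define when counting starts for them. The direction of any bias is unknown, and an onset rule in this trial would not by itself align the two windows.

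**Conclusion.** The point holds for the all-cause any, serious and Grade 3 or higher subject incidence rates in 12.4, and only for those. As written, they include events with onset between consent or consultation and the first fraction. A reader might conclude that the trial's main safety result is inflated, or that RT will be found more toxic than it is. That does not follow, because the RT-related rate in 12.1 excludes these events by both time window and attribution.

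The firm part of the size is arithmetic: 5 percentage points per affected subject at n = 20. The 6% to 15% addition to event counts rests on a constant event rate, an assumed RT course of 1 to 28 days and a 90-day follow-up. The incidence figures rest on assumed values of p and q, because the documents give no pre-RT event rate. The finding that the fatal table is unaffected assumes that the Safety paragraph of 12.4 uses treated subjects, as the primary analysis does.

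**What to change.** Add to the Safety paragraph of 12.4, in words such as: *Safety tables count adverse events with onset, or worsening in grade, on or after the first RT fraction. Events between consent and the first fraction are listed separately.* Attach this definition to the glossary term TEAEs, so that the term has a use.

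The rule must name the first RT fraction. The glossary sets Study Day 0 at the CAR T infusion, while Table 2 puts Day 0 at radiotherapy. Subjects enter with refractory disease 30 to 90 days after infusion, so a flag tied to the glossary's Day 0 would treat every pre-RT event as treatment-emergent and change nothing.

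The cost is small. Sample size, primary endpoint and visits are unchanged, onset dates are already collected, and no event is hidden because the earlier ones are still listed. The one added burden is that worsening of a pre-existing event needs a dated grade change on the case report form.

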7. ADVERSE EVENTS: LIST AND REPORTING REQUIREMENTS

7.1 Expected Toxicities

To date, the following important risks have been identified with axicel and tisacel: CRS, neurologic toxicities, infections, and cytopenias. Grading and management of these toxicities will be performed utilizing the recently released ASTCT CRS/ICANS grading system²¹. Please refer to the current product label for axicel, tisacel, lisocabtagene maraleucel, and brexucabtagene autoleucel for discussion of CRS and neurotoxicity (ICANS). Treatment with RT will occur after 30 day post-infusion period during which centers are FDA mandated to observe for peak toxicities. Additional information and management recommendations can also be found in appendix A. The following are important risks identified with radiation therapy but depend upon the target site for radiation therapy: dermatitis, pneumonitis, esophagitis, fatigue.

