9.7.5 Long-term Follow-up Period

All subjects who complete the study, and those who withdraw from the study after receiving RT for reasons other than death, will be asked to participate in the long-term follow-up portion of this study up to 12 months from CAR-T infusion, with a focus on long-term efficacy and safety. These patients will also have long-term follow-up as part of the FDA mandated CIBMTR CAR T cell therapy registry.

The following procedures will be completed for subjects who are enrolled at the time points of 6, 9, and 12 months following CAR-T infusion, as outlined in the SOA (Long-term Follow-up Period) Table 3:

- Physical exam
- CTCAE/PRO-CTCAE Surveys
- PET-CT/ Disease assessment at 6 and 12 months per standard of care
- Survival status
- Labs
 - CBC with differential
 - Cytokine levels
 - Lymphocyte subsets
 - Translational lab collection.
- Subsequent therapy for the treatment of NHL
- **Refer to Sections 8.4** for targeted adverse/serious adverse event reporting
 - Including neurological, hematological, infections, autoimmune disorders, and secondary malignancies
- Targeted concomitant medication documentation (for 12 months or until disease progression, whichever occurs first)
 - Including gammaglobulins, immunosuppressive drugs, anti-infectives, and vaccinations

Subjects may be contacted by telephone to confirm survival status and report targeted concomitant medication use.

If a subject progress in the LTFU phase, the subject will continue to be followed for survival status and subsequent therapy for the treatment of NHL. A translational lab sample and **serum (for cytokine evaluation)** should be collected at the time of progression as part of CAR T cell therapy protocol, prior to starting any subsequent anti-cancer therapy.

Should the subject fail to return to the clinic for a scheduled protocol specific visit, sites will need to make 2 attempts by a combination of telephone and mail to contact the subject. Sites must document both attempts to contact the subject. If a subject does not respond within 1 month after the second contact the subject will be considered lost to follow-up and no additional contact will be required.

As patients will be receiving commercial product, patients will also have long-term follow-up as part of FDA mandated CAR T cell therapy registry.

Table 2. Schedule of Assessments

Procedures	Screening	Enrollment & RT Planning	Radiotherapy		Post Radiotherapy Period			

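### From 3 months after RT the listed adverse event categories omit every RT risk the protocol names, so the safety tables may understate late non-serious RT toxicity; the collection windows also conflict

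*Combined protocol and SAP*

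**What the plan says.** Section 7.1 lists the important RT risks, which the protocol says exist "but depend upon the target site for radiation therapy: dermatitis, pneumonitis, esophagitis, fatigue".

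Section 7.4.1 sets two periods for AEs. All events "through 3 months after RT are monitored and reported". The requirement then narrows: "After 3 months, targeted adverse events including (eg, neurological, hematological, infections, autoimmune disorders, and secondary malignancies) will be monitored and reported", and this second period runs "for 6 months after treatment with axicel or tisacel or until disease progression, whichever occurs first". The same section ends non-serious AE reporting when a new anticancer therapy starts.

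Section 7.4.2 applies the same five categories to serious events, ends that period 6 months after RT or at progression, and adds one exception: "Serious events that the investigator assesses as related to RT should be reported regardless of the study period".

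Section 9.7.5, which instructs the long-term follow-up visits, repeats the list without the words that mark it as examples: "Including neurological, hematological, infections, autoimmune disorders, and secondary malignancies". Table 3 schedules targeted AEs/SAEs at Months 6, 9 and 12 after CAR-T infusion. Its footnote 7 gives a collection period of 24 months or until progression.

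Section 12.4 (Safety) states that "treatment related AEs reported throughout the conduct of the study will be tabulated by preferred term and system organ class".

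**The concern.** The trial exists to describe the toxicity of RT given after CAR-T therapy. Yet from 3 months after RT the AE list names none of the RT toxicities the protocol itself expects. A patient with, say, a Grade 2 in-field toxicity first seen at 5 months and managed as an outpatient fits no listed category and does not meet the serious-event exception.

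What is at stake is the late part of the safety record: the section 12.4 table of treatment-related AEs over the whole study, the comparison with historical controls in section 12.5, and the planning of the larger study, which section 12.2 bases on the events seen here. An event that was not recorded looks the same in those tables as an event that did not happen.

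**Working it through.** The plan gives no figure on this point to reproduce. The check sets the lists side by side, looks for other routes of collection, and does date arithmetic on the windows.

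**1. Overlap of the lists.** RT risks in 7.1: dermatitis, pneumonitis, esophagitis, fatigue. Targeted categories in 7.4.1, 7.4.2 and 9.7.5: neurological, hematological, infections, autoimmune disorders, secondary malignancies. Overlap: 0 of 4.

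**2. Is the list open?** In 7.4.1 and 7.4.2 it is given as examples; in 9.7.5 it is not. Section 7.4.2 needed a separate sentence to keep late serious RT-related events, which suggests that the targeted list was not taken to cover them. Section 7.4.1 has no matching sentence for non-serious events. So a site could report a late RT event, but nothing clearly requires it to.

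**3. Other routes after 3 months.**

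| Route | What it gives | What it lacks |
|---|---|---|
| CTCAE/PRO-CTCAE surveys at Months 6, 9, 12 (9.7.5, Table 3); patient items chosen by RT site (7.3) | Grades and symptoms at the visit | No stated onset and resolution dates or RT attribution; no rule that findings become AEs; events resolving between visits can be missed |
| Physical exams at Months 6, 9, 12 (Table 3); section 9.4 treats changes from baseline as AEs | A route to an AE record | Only what an exam shows; in tension with the targeted list |
| Follow-up of already reported AEs to stabilization or resolution (7.4.1) | Course of events with earlier onset | No late-onset events |
| Upgrade to serious as medically important (7.2.1) | An AE record without time limit if RT-related | At the investigator's discretion |

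Section 12.4 tabulates AEs by preferred term and system organ class and does not mention the surveys. For toxicity data, section 12.2 adds only pre/post-RT descriptive statistics with t-tests.

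**4. The 7.4.1 targeted window.** Inputs: refractory disease confirmed on day 30 to 90 after infusion (4.1); planning of 7 to 14 days (9.7.2); RT course of 1 to 28 days (assumption, since the documents give no length); no delay between confirmation and planning (assumption); 1 month = 30.44 days.

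The window opens at RT end + 91.3 days and closes at day 182.6. It is non-empty only if RT ends before 182.6 − 91.3 = day 91.3.

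RT end = confirmation day + planning + course. For day 30: 30 + 7 + 1 = 38 to 30 + 14 + 28 = 72.

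| Confirmed on | RT ends on day | All-AE period ends on day | Days left in targeted window |
|---|---|---|---|
| Day 30 | 38 to 72 | 129 to 163 | 53 to 19 |
| Day 60 | 68 to 102 | 159 to 193 | 23 to −11 |
| Day 90 | 98 to 132 | 189 to 223 | −7 to −41 |

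Negative values mean the window closes before it opens. If the 3 months are counted from RT start instead, a patient confirmed on day 90 still has no window: 90 + 7 + 91.3 = 188.3, which exceeds 182.6. In every row the Month 9 and 12 visits (about days 274 and 365) fall after the all-AE period.

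**5. Three different ends.** 6 months after axicel or tisacel (7.4.1), 6 months after RT for serious events (7.4.2), and 24 months (Table 3, footnote 7), although scheduled visits stop at Month 12. Table 3 also asks for targeted AEs at Months 9 and 12, after 7.4.1 has closed.

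**6. Scale.** With 20 subjects, one patient whose late event goes unrecorded changes an incidence by 1/20 = 5 percentage points.

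**The case against.** The strongest reply is that late RT toxicity is looked for. Toxicity surveys with patient items chosen by RT site run at Months 6, 9 and 12, exams run at the same visits, and section 9.4 makes changes on exam reportable. The targeted list is worded as examples in 7.4.1, and neurological events, hematological events and secondary malignancies are not exclusive to CAR-T; disease near the spinal canal or brain is a ground for treatment here. The event of most concern in section 12.2, Grade 4 or higher in the RT field, would be serious if life-threatening or fatal and so is kept without time limit if related to RT.

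Much of this stands. A reader might infer that late non-serious RT toxicity is not collected at all and will read near zero. The documents do not support that: the surveys and exams would pick up some of it, and no case report form is available to show what is asked. A reader might also infer a one-sided comparison in which late CAR-T events are fully recorded. That fails too, because under 7.4.1 the targeted window is short or empty for those events as well.

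What the reply does not supply is a rule that carries a late, non-serious RT finding into the AE record on which section 12.4 relies. Section 9.4 comes closest, but it covers only changes on exam and sits uneasily with the targeted list.

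**Conclusion.** The point holds in a limited form. After 3 months post-RT, late non-serious RT toxicity is not clearly required as an AE record with dates, grade and RT attribution. It is only partly captured elsewhere, and the section 12.4 tabulation of treatment-related AEs may understate it. The number of missed events cannot be estimated, because the documents give no late toxicity rate.

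The primary endpoint is not affected: section 12.1 closes it 30 days after RT, inside the all-AE period.

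The time after the all-AE period is long. Under the assumptions above it is (365 − 223)/(365 − 132) = 142/233 = 61% to (365 − 129)/(365 − 38) = 236/327 = 72% of the time from RT end to Month 12. A reader might take this as the share of toxicity data that is missing. It is calendar time on an assumed RT course, and surveys and exams fall within it.

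Separately, and as a matter of text alone, 7.4.1 leaves no targeted window for patients whose RT ends after about day 91, which eligibility up to day 90 makes likely for some. The three window ends cannot all apply.

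**What to change.** 1. In 7.4.1, 9.7.5 and Table 3, add to the targeted list: any AE, serious or not, in the irradiated field or assessed as related to RT.
2. State that CTCAE findings at the Month 6, 9 and 12 visits are entered as AEs with onset and resolution dates, grade and RT attribution, so that they reach the section 12.4 tables.
3. State that collection for this category runs to the last study visit and is ended neither by progression nor by new anticancer therapy, with the start of any new therapy recorded. Amend the 7.4.1 sentence that ends non-serious reporting at new therapy; otherwise it would contradict the new line.
4. Reconcile the window ends in 7.4.1, 7.4.2 and Table 3 footnote 7 with each other and with the Month 12 visit, and use one anchor date.

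Cost: text changes in several places, one added form category and some extra data entry at existing visits; no new visits or procedures. The real downside is that attribution to RT becomes harder once a new therapy has started, which is why its start date must be recorded.
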